2.0 OBJECTIVES AND SCIENTIFIC AIMS

2.1 Primary Objective

To compare the efficacy of different types of exercise training modalities, relative to progressive stretching (attention control group), on $VO_{2\text{peak}}$ in patients with advanced lung cancer or a history of operable lung cancer.

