Importantly, aerobic training will cause favorable adaptations in most O_2 transport components but will not reverse skeletal muscle atrophy/weakness, and will only partially reverse a more glycolytic fiber type distribution. Thus, aerobic training alone may be insufficient to ameliorate skeletal muscle dysfunction likely to manifest in lung cancer. Standard resistance training (i.e., activity involving the acute exertion of force) performed according to standard guidelines (i.e., 2-5 times/week, 50%-80% of one repetition maximum for 12-24 weeks) is unequivocally acknowledged as the most effective method to improve skeletal muscle function in human subjects.²⁴⁻²⁸ Moreover, in severely deconditioned adults, resistance training causes improvements in $\text{V}_{\text{O}_2\text{peak}}^{29-34}$, although the mechanisms underlying this effect are not clearly understood. In theory, while aerobic and resistance training might independently improve $\text{V}_{\text{O}_2\text{peak}}$ in lung cancer, such improvements are likely to be modest (~10%). Instead, the combination of aerobic and resistance training may be the most effective form of exercise training to optimally augment $\text{V}_{\text{O}_2\text{peak}}$. The complementary physiologic adaptations from the combination approach will result in higher cardiovascular O_2 delivery, skeletal muscle oxidative phosphorylation, muscle strength, and optimal fiber type composition, leading to higher muscle endurance, reduced fatigability, a higher threshold to the metabolic waste products of exercise, and reduced ventilatory requirements during exercise. This approach is hypothesized to maximize physiologic

adaptations in the principal factors underlying poor VO₂peak in lung cancer patients more effectively than either exercise modality alone.

Against this background, we designed the Lung Cancer exercise Training Study (LUNGevity), a randomized trial to investigate the efficacy of different types of exercise training in post-operative NSCLC patients. The protocol was amended in July 2017 to include patients with advanced (inoperable) lung cancer. The fundamental rationale for this multi-center trial is to identify the optimal type of exercise training to improve VO₂peak in lung cancer patients and understand the physiologic mechanisms underlying this effect.

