6.0 CRITERIA FOR SUBJECT ELIGIBILITY

6.1 Subject Inclusion Criteria

- Signed informed consent prior to initiation of study-related procedures
- Age 21-80
- Weight <205 kgs
- ECOG 1
- Diagnosed with histologically confirmed lung cancer, regardless of disease stage and receiving any prior line of any therapy in the context of metastatic disease
- An interval of at least three months following the completion of primary resection, if appropriate
- An interval of no longer than ten years following completion of primary therapy, if appropriate
- Life expectancy 4 months
- Performing less than 150 minutes of structured moderate-intensity or strenuous-intensity exercise per week.
- Exercise intolerance (i.e., patients must have a VO₂peak below that predicted for active age and sex-matched individuals)
- Willing to be randomized to one of the study arms
- Willing to commit to the study program and comply with all related protocol procedures
- Able to achieve an acceptable peak baseline CPET, as defined by any of the following criteria:
 - achieving a plateau in oxygen consumption, concurrent with an increase in power output;
 - a respiratory exchange ratio 1.10;
 - attainment of maximal predicted heart rate (HRmax) (i.e., within 10 bpm of age-predicted HRmax [HRmax = 220-Age[years]]);

- volitional exhaustion, as measured by a rating of perceived exertion (RPE) 18 on the BORG scale.
- Able to complete an acceptable baseline CPET in the absence of high risk ECG findings or other inappropriate response to exercise as determined by the PI.
- Ability to achieve and complete an acceptable baseline one-repetition maximum muscular strength test as defined by the effective execution of protocol-specific joint and muscle ranges of motion without remarkable signs or symptoms of pain, discomfort or distress.

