14.2 Primary and Secondary End Point Analyses

14.2.1 Primary End Point Analysis: The primary analysis will compare the efficacy of different types of exercise training modalities, relative to progressive stretching (attention control group), on $\text{v}_{\text{O}_2\text{peak}}$ in lung cancer.

An intent-to-treat statistical analysis will be conducted. Baseline characteristics will be compared using the Fisher exact test for categorical variables or a Wilcoxon rank sum test for continuous variables. The primary end point comparison will be analyzed using a multiple linear regression model to test for differences among and between the study arms in $\text{v}_{\text{O}_2\text{peak}}$ from baseline to follow up. The multiple linear regression model will include the baseline value of $\text{v}_{\text{O}_2\text{peak}}$, the stratification variables (i.e., chemotherapy treatment and sex), and study site.

In the absence of evidence to the contrary, multiple imputation strategies for missing Week 17 $\text{v}_{02\text{peak}}$ data will be performed assuming data were missing at random using linear regression. Results will be aggregated over 20 imputed sets using the variance formula by Rubin. In addition, a per-protocol analysis will be performed using a multiple linear regression model to test for differences among and between the study arms in $\text{v}_{02\text{peak}}$ from baseline to the post-intervention assessment (Week 17) on the basis of exercise attendance and adherence to the supervised exercise training in Arms A to C (<80% versus 80%).

14.2.2 Secondary End Point Analyses: As for the primary end point, the intention-to-treat principle will be employed for analysis of all secondary end points. Multiple linear regression models will be used to test for differences among and between the study arms in secondary end points from baseline to the postintervention assessment (Week 17). The multiple linear regression model will include the baseline value of $\text{v}_{02\text{peak}}$, the stratification variables (i.e., chemotherapy treatment and sex), and study site.

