15.2 Randomization

Participants will be randomly allocated, on an individual basis, to one of the four study arms. Randomly allocated participants will remain in the same group for the entire duration of the intervention (i.e., no cross-over). To ensure randomized groups are similar at baseline, patient randomization will be stratified based on whether their lung cancer was operable or inoperable, prior treatment with chemotherapy (yes vs. no) and sex (male vs. female). Chemotherapy causes significant reductions in $\text{v}_{02\text{peak}}$, thus it is important for groups to be balanced on this factor. Similarly, male participants have higher $\text{v}_{02\text{peak}}$ than female

participants and therefore is also expected to influence the effect of exercise training on $VO_{2\text{peak}}$ and other endpoints, thus it is important to ensure that groups are also balanced on this variable.

A permuted block design with allocation weight of 1:1: 1:1 is used to generate the treatment assignments. Following the successful completion of all baseline assessments, ExOnc research team personnel will enter randomization criteria into REDCap. Upon confirmation of stratification factors (chemotherapy treatment and/or sex) REDCap will electronically randomized the patient. Written confirmation of group allocation will be provided by email, a copy of which will be placed in the patient's case report form. The primary study RSA will then inform the participant of their group allocation.

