16.01 Role of Duke University Medical Center

This trial is a multi-site, randomized controlled trial comparing the effects of different exercise training interventions, relative to attention control, in patients with lung cancer following the completion of definitive adjuvant therapy. However, this trial represents a continuing effort that was first initiated at DUMC approximately 4 years ago by the principal investigator, [name]. Prior to his appointment at MSK in February 2014, [name] was a principal investigator at DUMC. During his tenure there, [name] secured a 5-year R01 grant from the National Cancer Institute to conduct the present study. During trial conduct, [name] accepted a position at MSK and hence all trial recruitment and study-related procedures were closed (all participants 'on trial' completed all study-related procedures but the study was closed to new patient enrollment).

IRB correspondence

All local IRB correspondence for DUMC that is initiated after the MSK protocol is open to accrual should be submitted to MSK. This includes but is not limited to approvals for amendments and continuing reviews as noted below. All other correspondence should be submitted to the local IRB according to local guidelines.

Amendments

Each change to the protocol document must be organized and documented by MSK and first approved by the MSK IRB/PB. Protocol amendments that affect MSK only (e.g. change in MSK Co-Investigator, MSK translation, etc.) do not require IRB review at the participating

site(s). All other protocol amendments will be immediately distributed to each participating site upon receipt of MSK IRB/PB approval.

Duke must obtain IRB approval for all amendments within 90 calendar days of MSK IRB/PB approval.

Continuing Review Approval

The Continuing Review Approval letter from the DUMC IRB and the most current approved version of the informed consent form should be submitted to MSK within 7 days of expiration.

Document maintenance

The MSK PI and the DUMC PI will maintain adequate and accurate records to enable the implementation of the protocol to be fully documented and the data to be subsequently verified.

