16.02 Current Status

As of September, 2013, the trial status is as follows: A total of 78 operable participants had been randomly allocated to four study arms: **Arm A**: supervised aerobic training (n=20), **Arm B**: supervised resistance training (n=20), **Arm C**: supervised combined aerobic and resistance training (n=19), and **Arm D**: progressive stretching (attention control group) (n=19). Of these, 70 (88%) participants successfully completed all study procedures, with 8 (12%) participants lost-to-follow-up. The mean adherence rate was 77% across Arms A to C, with minimal adverse events, suggesting that all intervention sessions are well-tolerated.

A total of 15 inoperable patients had been randomly allocated to four study arms: **Arm A**: supervised aerobic training (n=4), **Arm B**: supervised resistance training (n=4), **Arm C**: supervised combined aerobic and resistance training (n=4), and **Arm D**: progressive stretching (attention control group) (n=3).

Additional details are available. Overall, we were pleased with the study progress at the time of trial suspension and patient self-reports of the benefits of the trial.

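### Section 15.2 gives two different lists of stratification factors, and the models in 14.2.1 and 14.2.2 follow the list without operability; which list was used is not documented

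*Combined protocol and SAP*

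**What the plan says.** Section 15.2 describes stratification twice. Its opening paragraph says patients are "stratified based on whether their lung cancer was operable or inoperable, prior treatment with chemotherapy (yes vs. no) and sex". Its second paragraph, on the mechanics of allocation, says "Upon confirmation of stratification factors (chemotherapy treatment and/or sex) REDCap will electronically randomized the patient". The reasons 15.2 gives for stratifying cover chemotherapy and sex only.

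Sections 14.2.1 and 14.2.2 use the same covariate list for the primary and secondary models: baseline VO2peak, then "the stratification variables (i.e., chemotherapy treatment and sex), and study site". The *i.e.* makes this a closed list of two stratification variables. No section puts operability in a model or explains its absence.

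Operability matters to how the trial defines its population. The primary objective in 2.1 concerns VO2peak "in patients with advanced lung cancer or a history of operable lung cancer", and eligibility in 6.1 is "regardless of disease stage". Section 16.02 reports 78 operable and 15 inoperable patients randomized at Duke.

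**The concern.** The plan evidently means to adjust for the factors used in allocation, yet one factor that it names for allocation is missing from both models. Stratifying on a prognostic factor removes its contribution to the true variance of the arm contrasts. A model that leaves the factor out still counts that contribution in its residual variance, so its standard errors are too large and its tests conservative.

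Study site does not replace operability, because Duke enrolled both groups.

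Missing data raise a second issue. Section 14.2.1 imputes missing Week 17 VO2peak by linear regression under missing-at-random and does not list the imputation variables. If inoperable patients drop out more often and also change differently, an imputation model without operability may not satisfy that assumption.

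**Working it through.** **Comparing the text.**

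| Place | Factors named |
|---|---|
| 15.2, opening paragraph | operability, chemotherapy, sex |
| 15.2, REDCap sentence | chemotherapy and/or sex |
| 14.2.1 model | chemotherapy, sex (plus site) |
| 14.2.2 model | chemotherapy, sex (plus site) |

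Other sections do not settle the matter. Section 3.2 says "The protocol was amended in July 2017 to include patients with advanced (inoperable) lung cancer". Section 16.01 says that on the investigator's move (MSK appointment February 2014) "the study was closed to new patient enrollment" at Duke. Yet 16.02 states "A total of 15 inoperable patients had been randomly allocated to four study arms". Their split of 4/4/4/3 across Arms A to D is near balance, but does not show under which scheme they were allocated.

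**Inputs for the size of the effect.** From 14.1: SD of change 3.0 (variance V = 9), mean changes 0.60, 0.60, 2.10 and 0.0 in Arms A to D, first Holm step 0.05/3 = 0.0167 two-sided. From 1.0: 40 per arm. From 16.02: inoperable share so far 15/93 = 16%. The final share can lie between 15/160 = 9.4% (no MSK patient inoperable) and (15 + 67)/160 = 51.3% (all MSK patients inoperable).

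Assumed, because the documents give no figure: the operability effect on change, D = 1, 2 or 3 mL/kg/min, and the fraction R² of operability explained by the other covariates, 0 or 0.3.

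**The plan's own figure.** Simulating the stated design gives a probability of at least one significant contrast of 75.6% with pairwise t-tests, or 76.6% with a four-arm pooled variance, against the stated 80%. That gap is a separate matter. It does mean the comparisons below start from about 76 to 77%.

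**Residual variance inflation.** With b = p(1 − p)(1 − R²)D², inflation = b/(V − b). At p = 15/93, p(1 − p) = 0.1353. For D = 2:

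- R² = 0: b = 0.541; 0.541/8.459 = 6.4%.
- R² = 0.3: b = 0.379; 0.379/8.621 = 4.4%.

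For D = 1 and D = 3 the results are 1.5% and 15.6% at R² = 0, and 1.1% and 10.5% at R² = 0.3.

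**Power.** Simulation with operability exactly balanced across arms, smallest of three p-values below 0.0167, V = 9 and no missing data. At a 15% share (6 of 40 per arm):

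| D | Omitted / included, R² = 0 | Loss in points, R² = 0 | Loss in points, R² = 0.3 |
|---|---|---|---|
| 0 | no difference | 0 | 0 |
| 1 | 0.770 / 0.776 | about 0.5 | about 0.3 |
| 2 | 0.769 / 0.792 | about 2 | about 1.7 |
| 3 | 0.775 / 0.822 | about 5 | about 3.4 |

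Repeat runs agree to within about 0.3 points. At a 40% share the losses for D = 1, 2, 3 are about 1, 4 and 9 points at R² = 0, and about 0.5, 2.7 and 6.1 at R² = 0.3. The SD in 14.1 is for unadjusted change, so the fitted model may have a smaller residual variance. With an assumed variance of 6, power is already about 92%, and the losses at a 15% share and R² = 0 are about 0.4, 1.4 and 2.6 points.

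**Type I error.** With stratified blocks and a 16% share, familywise error was 0.039 with operability omitted and 0.048 with it included at D = 2, and 0.028 and 0.042 at D = 3 (2,500 trials each). With complete data, omission makes the tests conservative and does not inflate false positives.

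**The case against.** Three of the four statements agree on two factors, and the rationale in 15.2 covers only those two. If the REDCap build follows that list, the models already match the randomization, and the certain defect is one sentence in 15.2. This stands. A reader might infer that the models certainly omit a factor used in allocation, but the documents do not support that.

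The effect sizes are assumed, and two are large: D = 2 is close to the largest planned effect (2.10), and D = 3 is a full SD of change. Site and prior chemotherapy may absorb part of operability, so the losses at R² = 0 are on the high side. This also stands, and is why the R² = 0.3 figures are given.

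A reader might infer bias or false positives in the planned analysis. With complete data neither follows. Nor can both be ruled out outright once Week 17 values are imputed. Section 16.02 gives retention for the operable patients only (70 of 78 completed), so the size of that risk cannot be computed.

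The by-arm Duke counts differ between 1.0 (24/23/24/22) and 16.02 (24/24/23/22 when its two groups are added). A reader might take this as a bar to adjusting for operability. It is not: operability is coded patient by patient, and the mismatch is a separate point.

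It can also be said that adding operability when it was not used in allocation is only a covariate preference. Validity would indeed not require it. It would still gain precision if operability is prognostic, remove the effect of chance imbalance, and support the imputation.

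**Conclusion.** The inconsistency is certain; its consequence is conditional. Section 15.2 contradicts itself, both models follow the shorter list, and the documents do not show which list was operative. If operability was used in allocation and predicts change in VO2peak, the complete-data contrasts are unbiased but the tests are conservative. The power lost is small to moderate and depends on the assumed operability effect, the final inoperable share and the overlap with other covariates. If operability is unrelated to change, nothing is lost. A bias is possible only through missing Week 17 data, if operability predicts both dropout and outcome and is left out of the imputation; the documents give no basis for sizing it. The point should be acted on because the remedy is cheap and serves under either list, not because the planned analysis is shown to be invalid.

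**What to change.** 1. Check which factors were actually used in the randomization at Duke and at MSK, and make the two statements in 15.2 agree with what was done.
2. Before any unblinded analysis, add operability (operable vs inoperable, with a written coding rule) to the models in 14.2.1 and 14.2.2 and to the imputation model. If it was used in allocation, list it among the stratification variables. If it was not, keep the two-factor list and name operability separately as a prespecified baseline covariate.

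The cost is one degree of freedom per model, short edits to 14.2.1, 14.2.2 and 15.2, a check of settings at two sites, and coding of operability for the MSK patients. Duke status is already tabulated as 78 and 15. Sections 2.1 and 3.2 give a working meaning by setting advanced (inoperable) against operable disease, but an explicit rule is needed because entry is open to any stage.

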1.0 PROTOCOL SUMMARY AND/OR SCHEMA

Primary Objective: To compare the efficacy of different types of exercise training modalities, relative to progressive stretching (attention control group), on exercise capacity (V02peak) in patients with lung cancer.

[figure not shown]
Design: Patients with Memorial Sloan Kettering Cancer Center (MSK) histologically-confirmed lung cancer will be randomized to one of the following four arms: **Arm A:** supervised aerobic training; **Arm B:** supervised resistance training; **Arm C:** supervised combined aerobic and resistance training; and **Arm D:** stretching (attention control group).

The goal of this RCT is to recruit a total of 160 patients with histologically-confirmed lung cancer at any stage or receiving any type of therapy. A total of 40 per arm patients will be randomized in a 1:1:1:1 ratio to the four study arms.

This RCT was initially initiated and conducted at Duke University Medical Center (DUMC) by the principal investigator ([name]). The trial was suspended at DUMC (protocol-independent) due to change of the PI's institution ([name] is now at MSK). At the time of trial suspension, a total of 93 participants had been randomly allocated to the four study arms: **Arm A** supervised aerobic training (n=24), **Arm B**: supervised resistance training (n=23), **Arm C**: supervised combined aerobic and resistance training (n=24), and **Arm D**: progressive stretching (attention control group) (n=22)

At MSK, patients will be enrolled and randomized until target enrollment is met (67 patients in total at MSK): **Arm A:** supervised aerobic training (n=16), **Arm B:** supervised resistance training (n=17), **Arm C:** supervised combined aerobic and resistance training (n=16), and **Arm D:** progressive stretching (attention control group) (n=18); At the end of the trial, data will be analyzed for the pre-planned sample size (n=160).

Figure 1. Study Schematic for MSK Recruitment

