9.6 Concomitant Medications

All concomitant medications at the time of study entry will be identified through a medical chart review and recorded in REDCap. Participation in the study intervention must not impact use of concomitant medications at any stage of the study period.

9.7 Effects of Aerobic Training or Resistance Training on Exposure to Other Conventional/ Novel Anticancer Therapies

There is no clinical data on the effect of aerobic training and/or resistance training (or progressive stretching) on the therapeutic index of anticancer agents used in the management of lung cancer.. All clinical studies to date have focused on the effects of exercise training interventions to prevent and/or mitigate the psychosocial and/or physiological side-effects of cancer therapy; whether exercise training influences the pharmacodynamics (PD) or pharmacokinetics (PK) of anticancer therapy has not been investigated.

9.8 Effects of Conventional/Novel Anticancer Therapies on Aerobic Training or Resistance Training

Our group, as well as others, have demonstrated that different forms of anticancer therapy causes unique and varying degrees of damage to various components of the cardiopulmonary system (heart-lung-blood-muscle axis). Collectively, these effects lead to significant and marked declines in global cardiopulmonary function, manifest as poor exercise tolerance (decreased V_{O2peak}). A major rationale for this trial is to determine the optimal exercise training modality to mitigate and/or reverse this phenotype in patients with lung cancer.

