14.0 BIOSTATISTICS

14.1 Sample Size Calculation and Justification

This randomized phase trial will accrue 67 subjects with lung cancer over an accrual period of ~36 months. The primary analysis will compare the efficacy of different types of exercise training modalities, relative to progressive stretching (attention control group), on $\text{v}_{\text{O}_2\text{peak}}$. Three separate t-tests will be used to compare each exercise training arm to the attention-control arm in mean change across time for $\text{v}_{\text{O}_2\text{peak}}$. The overall alpha level will be controlled at a two-sided 0.05 by using Holm's procedure.⁵⁶ That is, Holm's procedure first ranks the three p-values from lowest to highest. The first (lowest) p-value has to be less than 0.05/3 (0.0167) to be significant and permit continuation to the other t-tests. The Holm's procedure continues sequentially in this fashion using alpha levels of 0.05/2 (0.025) and 0.05/1 (0.05) for the remaining two t-tests, respectively. Power for this study is defined as the probability that at least one of the three t-tests of the arm effect on $\text{v}_{\text{O}_2\text{peak}}$ is significant; in other words, power is the probability that the first of the 3 ordered t-tests are significant. We assume that change in $\text{v}_{\text{O}_2\text{peak}}$ will have a standard deviation of $3.0 \text{ mL}\cdot\text{kg}^{-1}\text{min}^{-1}$. Statistical power depends upon the configuration of mean change in $\text{v}_{\text{O}_2\text{peak}}$ across the 4 arms. Thus, for example, 80% power is obtained when the mean change in $\text{v}_{\text{O}_2\text{peak}}$ across Arms A, B, C, and D is 0.60, 0.60, 2.10, and 0.0 ($\text{mL}\cdot\text{kg}^{-1}\text{min}^{-1}$), respectively.

A final important consideration when conducting exercise RCTs, is extent of exercise 'drop-in' or contamination in Arm D. In other words, the concern is that patients assigned to attention control independently initiate an exercise training program which, in turn, potentially dilutes the efficacy of aerobic training on the outcomes of interest. However, we feel this is less of a concern in the present study because patients (in the exercise training arms) will be provided with supervised, individualized training prescriptions (which will be difficult to replicate without sophisticated prescription algorithms and expertise) and attention-control participants are also provided with a supervised attention intervention.

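### The primary and secondary models leave out operability, a named stratification factor, and systemic therapy at entry; adding both is a cheap gain in precision

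*Combined protocol and SAP*

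**What the plan says.** **Population.** Section 1.0 recruits patients with "histologically-confirmed lung cancer at any stage or receiving any type of therapy". Section 6.1 accepts any stage and any line of therapy in metastatic disease, and allows up to ten years since primary therapy. No exclusion in Section 6.2 bars current treatment of the lung cancer. Section 3.2 says the trial was designed for post-operative patients and amended in July 2017 to add advanced (inoperable) disease. Section 16.02 already counts 15 inoperable patients among the 93 randomised at the first site. Sections 16.01 and 16.2 still describe the trial as one "in patients with lung cancer following the completion of definitive adjuvant therapy".

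**Effect of therapy.** Section 9.8 says of the damage done by different anticancer therapies: "Collectively, these effects lead to significant and marked declines in global cardiopulmonary function". Section 15.2 gives the effect of chemotherapy on VO2peak as its reason for stratifying on it.

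**Strata.** Section 15.2 names three factors: operable or inoperable disease, then "prior treatment with chemotherapy (yes vs. no) and sex (male vs. female". Its later sentence on REDCap mentions only chemotherapy and sex.

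**Model.** Sections 14.2.1 and 14.2.2 use a linear regression with baseline VO2peak, "the stratification variables (i.e., chemotherapy treatment and sex), and study site".

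**Data held.** Section 9.6: "All concomitant medications at the time of study entry will be identified through a medical chart review and recorded in REDCap". Table 1 also has a medical history at screening. No analysis uses either.

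**The concern.** By the protocol's own reasoning, anticancer therapy matters for the primary endpoint, yet the only treatment variable in the model is chemotherapy, stratified as prior chemotherapy yes or no. That variable puts a patient whose chemotherapy ended years ago with one receiving it now. It also codes as no a patient who is on another systemic therapy and never had chemotherapy. Operability, the stratum most closely tied to being on treatment, is dropped from the model.

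If patients on therapy have a different expected change over 16 weeks in every arm, and the model has no term for it, that difference stays in the residual variance of all three comparisons with stretching. The stake is power, in a trial with 40 patients per arm.

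**Working it through.** **Inputs from Section 14.1 (and 40 per arm from Section 1.0).** Mean changes are 0.60, 0.60, 2.10 and 0.0 mL/kg/min in Arms A to D, with an SD of change of 3.0. On error rate: "The overall alpha level will be controlled at a two-sided 0.05 by using Holm's procedure". On the first step: "The first (lowest) p-value has to be less than 0.05/3 (0.0167) to be significant". Power means at least one significant comparison with Arm D.

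**The plan's own figure.** The standard error of a difference is 3.0 × √(2/40) = 0.671, so C against D has a standardised effect of 2.1/0.671 = 3.13. Power for C against D alone is 75.1%. Simulating all three t-tests (200,000 trials) gives 75.6% for at least one, or 76.5% with a variance pooled over four arms. The plan states 80%, which these inputs do not reproduce. That is a separate matter; here it only fixes the base at about 76%.

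**Inputs not in the documents (assumed).** p is the share on systemic therapy at entry. b is how much less VO2peak changes, in mL/kg/min, in patients on therapy, equally in every arm. As an upper bound on p, if only the 15 inoperable first-site patients and the 67 second-site patients could be on therapy, p is at most (15 + 67)/160 = 51%.

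**Formula.** If 3.0 is the SD among patients with the same therapy status, omitting the term gives an SD of √(9 + p(1−p)b²). For p = 0.3 and b = 2 this is √(9 + 0.21 × 4) = √9.84 = 3.14.

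**Regression with baseline VO2peak.** Simulated with 160 patients, residual SD 3.0, and all on-therapy patients among an assumed 40% inoperable. Entries are power for at least one significant comparison.

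| p | b | neither term | operability only | therapy at entry only | loss from omitting therapy (points) |
|---|---|---|---|---|---|
| 0.2 | 1 | 75.6% | 75.2% | 76.2% | 0.6 |
| 0.2 | 2 | 73.3% | 74.1% | 76.2% | 2.9 |
| 0.2 | 3 | 70.0% | 72.1% | 76.2% | 6.2 |
| 0.3 | 1 | 75.2% | 75.3% | 76.1% | 0.9 |
| 0.3 | 2 | 72.3% | 74.1% | 76.1% | 3.8 |
| 0.3 | 3 | 68.0% | 72.5% | 76.1% | 8.1 |

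At b = 0 there is no gain. Each entry rests on 4,000 trials, so its simulation standard error is about √(0.76 × 0.24/4000) = 0.7 points. The models were fitted to the same simulated data, so differences within a row are steadier than that.

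**A larger share, with site in the model.** Take p = 0.4, spread evenly over the 82 patients above. Raw t-tests give 70% at b = 2.1 and 65% at b = 3. Adding site, which the plan does include, lifts these to 72.6% and 69.5%. Against 75.7% without any therapy effect, the losses are 3.1 and 6.2 points, in line with the table.

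**The case against.** Much of the case on the other side stands.

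- **Allocation is not blind to treatment status.** A reader of Section 14.2 might infer that the strata record only prior chemotherapy. Section 15.2 also names operability, a partial proxy for being on treatment. The plainer defect is that the model drops it. Operability alone recovers part of the loss: 74.1% at b = 2, against 76.1 to 76.2% with the therapy term.
- **The cited evidence concerns level, not change.** Sections 9.8 and 15.2 say that therapy lowers VO2peak. Baseline VO2peak is in the model and largely absorbs a deficit already present at entry. No section quantifies a further decline during the 16 weeks. An effect of 2.1 would equal the whole benefit assumed for Arm C.
- **Raw t-tests overstate the loss.** Power of 65 to 70% belongs to an analysis without site or baseline, not to the planned model.
- **Chance imbalance is not a second harm.** At p = 0.4 and b = 2.1 its SD is 2.1 × √(2 × 0.24/40) = 0.23. This is already in the wider error: √(0.671² + 0.230²) = 0.709 = 3.171 × √(2/40). It is not a bias.
- **Section 14.1 may mean 3.0 as the total SD.** Then nothing is lost against plan, and adjustment is a gain. By t-test at b = 2, power would rise from 75.6% to 79.1% (p = 0.2) or 80.2% (p = 0.3).
- **One yes/no variable pools unlike agents**, which Section 9.8 says differ in their damage. True, but it still separates current treatment from none.

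What survives is that both terms are missing, that they come from facts fixed before randomisation, and that the protocol itself gives the reason to include them.

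**Conclusion.** The models in Sections 14.2.1 and 14.2.2 omit a named stratification factor and the treatment status that the protocol's own rationale points to. A reader might infer that the treatment comparison is biased or its type I error inflated. The documents do not support that: leaving a pre-randomisation covariate out of a linear model keeps the randomised comparison unbiased, and the only cost is precision.

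That cost is about 1 point of power if therapy lowers the 16-week change by 1 mL/kg/min, about 3 to 4 points at 2, and about 6 to 8 points at 3, from a base of about 76%. These figures assume 20 to 40% of patients on therapy, the same therapy effect in every arm, and 3.0 as the SD within therapy groups. Neither the share nor the effect is in the documents, and if therapy does not alter the trajectory the gain is nil. This is a cheap improvement, not an error in the design.

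**What to change.** In Sections 14.2.1 and 14.2.2, in both the regression and the imputation models:

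1. List operability (operable or inoperable) with chemotherapy and sex as a stratification variable, and bring the REDCap sentence in Section 15.2 into line with the three factors named there. If operability was not used at allocation for some patients, it is still a valid baseline covariate.
2. Add one prespecified baseline covariate: receiving systemic anticancer therapy at randomisation (yes/no). Code it before unblinding from the entry medical history and the concomitant-medication record. For the 93 first-site patients, use the chart abstraction that Section 16.04 keeps open.

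The cost is two degrees of freedom, a sentence or two in the analysis section, and some abstraction work. At no therapy effect the simulated power is essentially unchanged by the therapy term (76.2% either way at p = 0.2; 76.3% to 76.1% at p = 0.3). Allocation does not change. Fixing both terms in advance also prevents a later choice of covariates guided by the data in an open-label trial.
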